### **Data collection**

In each country, individuals were surveyed by trained interviewers through face-to-face interviews using a structured standardized questionnaire. Data collection was coordinated by DOXA, a leading market research organization and Italian branch of the Worldwide Independent Network/Gallup International Association (WIN/GIA), and performed in collaboration with its European partners (see “Selection of the subcontract or performing data collection” paragraph). Data was collected within computer assisted personal interviews (CAPI). The fieldworks lasted two to three months in each country. The English version of the questionnaire has been developed by collaborators from University of Nottingham (UK) University of Regensburg (Germany), and Mario Negri Institute (Italy). Before fieldwork, the tinnitus-related questions were translated from English into various country-specific languages using the good practice guidelines for questionnaire translation. The details of the translation process have been published as a technical note.

The country-specific information provided by DOXA and its European partners for each European country include information on sampling methodology (e.g., sampling method used, response rate, fieldwork dates, age range). The survey questionnaire is designed to collect individual-level information for each survey participant, and is divided in two sections. The first section provided information on: socio-economic and demographic characteristics (e.g., sex, age, level of education, and profession). The second section provided information on tinnitus prevalence, tinnitus severity, healthcare resource use for tinnitus, and hearing difficulty prevalence.

### **Statistical analysis plan**

#### Creation of the survey dataset

Once the fieldwork was completed, DOXA collected data from its European partners and after internal checks provided to Mario Negri Institute the 12 anonymous data files in text format, with the corresponding codebook in English language. The 12 data files were managed by the team at the Laboratory of Lifestyle Epidemiology, Department of Environmental Health Sciences of Mario Negri Institute. Using the statistical package SAS, version 9.4 (SAS Institute, Cary, NC, USA), they performed the input of the 12 textual data file into 12 corresponding SAS datasets, and then created a unique final dataset in SAS. This dataset was checked for coherence and for the presence of possible errors, cleaned, and finalized through the generation of queries which were addressed by DOXA and its European partners.

#### Statistical analyses

Statistical analyses required to achieve objectives has been conducted by the teams from the Laboratory of Lifestyle Epidemiology, Department of Environmental Health Sciences of Mario Negri Institute and the University of Nottingham, using SAS statistical package. Prevalence of three working definitions of tinnitus (any, bothersome and severe tinnitus) have been estimated through univariate statistical analyses (i.e., descriptive statistics for categorical data, including absolute or relative frequencies), overall, by country, and in strata of selected demographic and socio-economic (individual and country-specific) characteristics. Continuous variables have been summarized through the use of means and standard deviations. Alternatively, they have been categorized, and thus described through absolute or relative frequencies.

Multivariate analyses have been conducted to identify sub-groups of the population (e.g., based age-groups, low vs. high educated subjects) or clusters of countries (e.g., based on income levels and regional groups) where tinnitus is more frequent. Thus, odds ratios (OR), and the corresponding 95% confidence intervals (CI), were estimated through logistic regression models after adjustment for selected individual-level characteristics.

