## **BACKGROUND AND RATIONALE**

Tinnitus is a common symptom of clinically heterogeneous pathologies and is defined as the conscious perception of an auditory sensation in the absence of a corresponding external stimulus. Tinnitus, in its debilitating form, negatively affects emotional health and social well-being, and can precipitate psychological distress severe enough to cause self-harm and suicidal ideations, while exerting substantial individual and societal financial burden. Therefore, it becomes crucial to take adequate preventive measures and health interventions. According to population-based studies from Western Europe and US, tinnitus prevalence lies between 10% and 15%. Nonetheless, there is a lack of clear understanding of global prevalence of tinnitus. Inherent methodological drawbacks and between study differences hinder deriving a global estimate by pooling data from studies conducted in different countries and world regions. Therefore, uncertainties with regards to the prevalence of tinnitus remain.

Being a subjective condition, the impact of tinnitus symptoms depends on its perceived bothersomeness or severity. Therefore, "bothersome" or "severe" tinnitus symptoms are a better predictor for the emotional, societal and financial burden of tinnitus than "any" tinnitus. The economic burden is directly related to the severity of the tinnitus symptoms, with increased healthcare costs in people with severe tinnitus. In a study conducted in the Netherlands, the mean annual costs per patient was €767 for mild, €1329 for moderate and €2218 for severe tinnitus. A similar pattern was noted in a study in USA, where medical costs were reported to be directly proportional to severity of tinnitus. While epidemiological studies have attempted to distinguish any and severe tinnitus, both these concepts are troubled by heterogeneous prevalence estimates. Hearing difficulty is a major risk factor for tinnitus and often co-occur in an individual. However, not many studies have measured the prevalence of tinnitus in a population with hearing difficulty.

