## **OBJECTIVE**

The primary objective of this population-based cross-sectional study is to estimate the overall and country specific prevalence of any tinnitus, bothersome tinnitus, and severe tinnitus in 12 European Union (EU) countries.

The study data have been analyzed to fulfil the following secondary objectives:

- To examine inter-country differences in prevalence of tinnitus by making the following comparisons:
  - Comparing prevalence estimates in countries with relatively low versus high gross domestic product (GDP) per capita
  - Comparing prevalence estimates in countries within different European regions (i.e., Northern, Southern, Eastern and Western Europe)
- To understand the effect of sex, age, socio-economic variables, body mass index (BMI), and marital status on overall prevalence of tinnitus
- To assess the effect of hearing difficulty on tinnitus prevalence
- To explore the effect of tinnitus severity on use of healthcare resource for tinnitus

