## METHODS

### Study design

To achieve the aims of this study, we conducted face-to-face population-based cross-sectional survey in 12 strategically selected EU28 countries (Bulgaria, England, France, Germany, Greece, Ireland, Italy, Latvia, Poland, Portugal, Romania, and Spain). The study methodology is similar to another Pan-European survey on second-hand smoking and e-cigarettes, the TackSHS Project (“Tackling secondhand tobacco smoke and e-cigarette emissions: exposure assessment, novel interventions, impact on lung diseases and economic burden in diverse European populations”; [www.tackshs.eu](http://www.tackshs.eu)) conducted in the same 12 countries in 2017-2018, funded by the European Commission (EC) within the Horizon 2020 research grants (grant agreement number: 681040).

For each country, the study sample is representative of the general population aged 18 years and above in terms of age, sex, geographic area, and socio-economic characteristics. Multi-stage methodology was used as the preferred sampling methodology. In the first stage, the primary unit of selection was geographic area or voting center. In the second stage, households or municipalities were selected. In the last stage, respondents were chosen randomly, in order to be representative of the population. Other methods, including stratified or simple sampling or quota methods, were also accepted wherever it is not possible to conduct a multistage random sampling.

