### Selection of countries

For the present study, an appropriate sample of 12 European countries—all EU28 Member States (MS)—representing geographical, legislative and cultural variations across the EU, have been selected. The selected European countries are as follows: Bulgaria (BG), England (UK), France (FR), Germany (DE), Greece (GR), Ireland (IE), Italy (IT), Latvia (LV), Poland (PL), Portugal (PT), Romania (RO), and Spain (ES). These countries were selected after taking into account several aspects, including: i) different geographical distribution; ii) different level of per capita income. According to geographic area, we considered countries from northern (IE, UK), central/western (DE, FR), central/eastern (BG, LV, PL, RO), and southern Europe (ES, IT, GR, PT). Moreover, the selection includes the 7 most populated EU28 MS (DE, ES, FR, IT, UK, PL, RO), and, among less populated countries, we prioritized middle-income countries (BG, RO). Overall, the 12 selected EU MS represent 78.8% of the EU28 overall population.

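### GDP-group and region comparisons rest on 12 countries, but the only model described treats 11,427 respondents as independent evidence

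*Combined protocol and SAP*

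**What the plan says.** The Objective section lists, as a secondary aim, "Comparing prevalence estimates in countries with relatively low versus high gross domestic product (GDP) per capita", and a parallel comparison across Northern, Southern, Eastern and Western Europe. Under Statistical analyses, multivariate work is to identify sub-groups of people or "clusters of countries (e.g., based on income levels and regional groups) where tinnitus is more frequent". The next sentence gives the method for both: odds ratios and 95% confidence intervals "were estimated through logistic regression models after adjustment for selected individual-level characteristics".

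The Selection of countries section assigns the 12 countries to regions: 2 northern, 2 western, 4 eastern and 4 southern. The Study population section gives a final sample of 11,427. No section mentions a random effect, GEE, cluster-robust variance, survey procedure or country-level analysis.

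The document also shows ways in which countries could differ apart from wealth or region. On sampling, "Other methods, including stratified or simple sampling or quota methods, were also accepted" where multistage random sampling was not possible. On measurement, "the tinnitus-related questions were translated from English into various country-specific languages".

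**The concern.** GDP group and region have no within-country variation. Interviewing more people in Latvia sharpens the estimate for Latvia. It does little to show whether Latvia's level reflects its GDP, its region or something particular to Latvia. A single-level logistic model ignores this and computes the standard error as if each respondent were a separate observation of the effect of GDP or region. Adjusting for individual characteristics removes only the country differences that those covariates explain.

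At stake is one secondary objective. A gap that merely reflects which countries fell into which group could be reported as a GDP or regional gradient with a tight interval. The Relevance and Implications section expects the study's estimates to guide resource allocation, so such a gradient could mislead.

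**Working it through.** **The plan's own precision figure.** The Sample size computation section states a maximum standard error below 1.6% per country. With p = 0.5 and n = 1,000, √(0.25/1000) = 1.58 points, which reproduces it. At the achieved mean of 11,427/12 = 952 the value is 1.62 points, marginally above. Either way, this describes sampling error within one country and says nothing about a contrast between groups of countries.

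**Inputs from the documents.** 12 countries; 11,427 respondents; regions of 2, 2, 4 and 4 countries; 95% intervals. A prevalence of 12% was chosen from within the 10% to 15% cited in Background and Rationale.

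**Assumptions not in the documents.** Between-country SD on the logit scale (0 to 0.3); 1.5% prevalence for a rare outcome such as severe tinnitus; a 6 v 6 GDP split; equal country sizes of 952; no true GDP or region effect; no covariates. Adjustment may change the residual SD.

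**Analytic check.** True SE divided by single-level SE ≈ √(1 + SD² × 952 × p(1 − p)). At p = 12%, 952 × 0.12 × 0.88 = 100.5, so:
- SD 0.1: √(1 + 1.005) = 1.42
- SD 0.2: √(1 + 4.02) = 2.24
- SD 0.3: √(1 + 9.05) = 3.17

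The actual size of the 5% test is 2 × [1 − Φ(1.96/ratio)], which gives 17%, 38% and 54%.

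**Simulation.** 20,000 surveys per scenario; Wald test of the pooled log odds ratio for GDP, and a 3-df chi-square for region:

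| Prevalence | Logit SD | SE ratio (GDP) | Rejection, GDP | Rejection, region | Coverage of 95% CI, GDP |
|---|---|---|---|---|---|
| 12% | 0 | 1.0 | 5% | 5% | 95% |
| 12% | 0.1 | 1.4 | 17% | 27% | 83% |
| 12% | 0.2 | 2.25 | 38% | 67% | 62% |
| 12% | 0.3 | 3.2 | 55% | 86% | 45% |
| 1.5% | 0.1 | 1.07 | 7% | 8% | 93% |
| 1.5% | 0.2 | 1.27 | 12% | 17% | 88% |
| 1.5% | 0.3 | 1.54 | 20% | 34% | 80% |

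GDP splits of 3 v 9, 4 v 8, 5 v 7 and 6 v 6 all give 38% to 39% at 12% prevalence and SD 0.2.

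**What the SDs mean.** logit(0.12) = −1.992. Adding ±1.96 × 0.1 gives country prevalences of about 10.1% to 14.2%; ±1.96 × 0.2 gives about 8.4% to 16.8%.

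**An anchor, for illustration only.** logit(0.15) − logit(0.10) = 0.463. If the cited range were ±2 SD, the SD is 0.463/4 = 0.12 and rejection is 20% for GDP and 34% for region. If it were ±1 SD, the SD is 0.463/2 = 0.23 and rejection is 44% and 75%.

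**Country as the unit.** On the 12 country log-odds, the t-test for GDP (10 df) rejected in 4.7% to 5.3% of surveys and the F-test for region (3, 8 df) in 4.8% to 5.3%, in every scenario. A random-intercept logistic model with 10 and 8 df (2,000 runs each) gave 4% to 5% for GDP and 3% to 5% for region at 12% prevalence. At 1.5% it gave 2% to 4% and 1% to 3%, which is conservative.

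**The case against.** The strongest reply is that the plan only describes named countries. For GDP and region the Objective section speaks of comparing prevalence estimates, whereas it uses the word effect for sex, age and hearing difficulty. The countries were chosen deliberately and cover 78.8% of the EU28 population, so they are not a random sample. If they are fixed strata, between-country variation does not enter and the single-level intervals are valid for that description. This stands, and it is why the primary prevalences in the same 12 countries are not criticised. But grouping countries by GDP or region invites a statement about GDP or region. In the simulation the labels carry no information, so an arbitrary split of the 12 countries would give an interval excluding 1 just as often.

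Second, the size is not documented. The 10% to 15% range comes from different studies whose methods differ, whereas this survey used one questionnaire. Reading it as ±1 SD is generous: 12 normal values span about 3.26 SD on average, so SD = 0.463/3.26 = 0.14. That objection is fair, but rejection at that SD is still about 26% for GDP and 46% for region.

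Third, the analysis section is short and clustering may have been handled without being reported. That is possible, and the point is limited to the model as written.

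Fourth, if sampling method or question wording lines up with region or GDP, the result is bias, which a random intercept does not remove. This also stands: the fix corrects the intervals, not confounding between countries.

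**Conclusion.** The concern holds. The plan ties a single-level logistic model to exposures carried by 12 countries, and nothing in the document allows for that. The direction is certain: any residual between-country variation makes these intervals too narrow for inference about GDP or region. The amount is conditional on an SD the documents do not give. At about 12% prevalence, even an SD of 0.1 more than triples the nominal error rate for GDP and raises the rate for region more than fivefold. For a rare outcome the inflation is smaller. The point is confined to one secondary objective. The overall and country-specific prevalences are not affected, and this design effect does not apply to the odds ratios for individual characteristics such as sex, age and education. It should be fixed.

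**What to change.** For GDP group and region only, fitted one at a time, keep the individual-level covariates and do one of the following:
- add a random intercept for country with small-sample degrees of freedom (12 − 2 = 10 for low v high GDP, 12 − 4 = 8 for four regions); or
- regress the 12 country-level adjusted log-odds on the grouping. Prefer this for a rare outcome such as severe tinnitus, where the random-intercept model was conservative.

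State that these contrasts rest on 12 countries. If single-level odds ratios are also shown, label them as descriptive of these countries. Keep the planned low/high GDP comparison; GDP as a continuous variable is an optional supplement. The document reports the analyses as done, so mark the re-analysis as post hoc.

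The effort is a few lines of text and one extra SAS procedure on existing data. The statistical cost is wider intervals: at 12% prevalence and SD 0.2, a null GDP odds ratio would typically carry an interval of 0.76 to 1.32 instead of 0.89 to 1.12. Power of the country-level GDP test at 12% prevalence:

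| Logit SD | OR 1.2 | OR 1.3 | OR 1.5 |
|---|---|---|---|
| 0.1 | 54% | 84% | >99% |
| 0.2 | 25% | 46% | 82% |
| 0.3 | 14% | 26% | 53% |

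At 1.5% prevalence and an odds ratio of 1.5, power is 67%, 51% and 37% at the three SDs. The precision given up was not real for statements about GDP or region.

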### Study population

In each of the 12 selected European countries, approximately 1000 individuals, representative of the general population aged 18 years and above in terms of age, sex, geographic area, and socio-economic characteristics, were enrolled in this cross-sectional study. The final sample therefore includes a total of 11,427 subjects.

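### The plan gives no country term for the pooled 12-country logistic models, so individual-level odds ratios may mix within- and between-country differences and the GDP and region intervals may be too narrow

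*Combined protocol and SAP*

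**What the plan says.** The regression plan is one short paragraph under Statistical analyses. Odds ratios with 95% confidence intervals "were estimated through logistic regression models after adjustment for selected individual-level characteristics". The same paragraph uses these models for two kinds of question: subgroups of people, such as age or education groups, and "clusters of countries (e.g., based on income levels and regional groups) where tinnitus is more frequent".

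The exposures of interest come from the Objective section: "To understand the effect of sex, age, socio-economic variables, body mass index (BMI), and marital status on overall prevalence of tinnitus", and "To assess the effect of hearing difficulty on tinnitus prevalence".

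On the structure of the data:

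- Study population: "In each of the 12 selected European countries, approximately 1000 individuals" were enrolled, so country is a design stratum.
- Creation of the survey dataset: the team read in the 12 national files and "created a unique final dataset in SAS".
- Selection of countries: the countries were picked as "representing geographical, legislative and cultural variations across the EU", with per capita income as one criterion.
- Study design: the sampling method was allowed to differ between countries.

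For the descriptive tables, prevalence is given overall, by country, and "in strata of selected demographic and socio-economic (individual and country-specific) characteristics". The documents mention no country fixed effect, country random effect, stratified model or clustered standard error for the regressions.

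**The concern.** There are two separate problems, because the one description serves two kinds of contrast.

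**Individual-level factors.** Suppose low education, high BMI or hearing difficulty is more common in some countries, and those countries also report more (or less) tinnitus for other reasons. A pooled model without country then adds the between-country pattern to the within-country association. It could show an association that exists in no country, or hide one that does. With 11,427 respondents the interval around the wrong value would be narrow. Such differences are foreseeable: the countries were chosen to differ in income, the questions were translated into several languages, and sampling methods could vary.

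**GDP and region.** Here the exposure is a property of the country, so the effective number of units is 12, not 11,427. A model that treats respondents as independent within country leaves out the variation between countries in the same group, and its intervals are too short if that variation exists.

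**Working it through.** **The plan's own figure.** The only design figure is a maximum standard error below 1.6% per country (Sample size computation). With SE = √(p(1−p)/n) at p = 0.5 and n = 1000, SE = √(0.25/1000) = 1.58%, which reproduces it. At the achieved mean of 11,427/12 = 952 it is 1.62%. Nothing below depends on this figure.

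The documents give no prevalence or exposure share by country. All inputs below are therefore assumptions, except N = 11,427 and the 10% to 15% background prevalence, which comes from Background and Rationale.

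**Check 1: two blocks of countries, no association in any country.** Half the sample has prevalence p1 and exposure share e1, the other half p2 and e2. The pooled cells are a = (p1e1 + p2e2)/2 for exposed cases, and likewise b (exposed non-cases), c (unexposed cases) and d (unexposed non-cases). The odds ratio is ad/(bc), and SE(log OR) = √[(1/a + 1/b + 1/c + 1/d)/N].

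For the first row: a = 0.0525, b = 0.3475, c = 0.0725, d = 0.5275. OR = (0.0525 × 0.5275)/(0.3475 × 0.0725) = 1.10, with SE 0.057.

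| Prevalence | Exposure share | Pooled OR (true value 1.00) | 95% CI |
|---|---|---|---|
| 10% v 15% | 30% v 50% | 1.10 | 0.98–1.23 |
| 10% v 15% | 20% v 60% | 1.21 | 1.08–1.35 |
| 10% v 15% | 50% v 30% | 0.91 | 0.81–1.02 |
| 10% v 20% | 30% v 50% | 1.18 | 1.06–1.30 |
| 10% v 20% | 20% v 60% | 1.38 | 1.24–1.53 |

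The blocks are perfectly aligned, which favours bias. Even so, two of the five results are not significant.

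**Check 2: 12 countries varying continuously.** There are 12 equal-sized countries. In a typical country 35% are exposed and 15% of the unexposed have tinnitus. Country effects are on the logit scale, with SD sy for tinnitus, SD sx for exposure and correlation r between them. The expected odds ratio without a country term is:

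| sy, sx | r | True OR 1.00 becomes | True OR 1.50 becomes |
|---|---|---|---|
| 0.2, 0.3 | −0.5 to 1 | 0.97–1.06 | 1.45–1.59 |
| 0.4, 0.6 | −0.5 to 1 | 0.89–1.25 | 1.32–1.85 |
| 0.6, 0.6 | −0.5 to 1 | 0.84–1.38 | 1.24–2.02 |

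If sy = 0 or sx = 0, a null odds ratio stays at 1.00. At r = 0 it stays between 0.996 and 1.004.

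**Check 3: a country-group contrast.** The 12 countries are split 6 v 6, with prevalence 12.5% and between-country logit SD s within each group.

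- Variance of the log odds ratio if country is ignored: 2/(5713.5 × 0.125 × 0.875) = 0.0032, so SE = 0.057.
- Actual variance: 0.0032 + 2s²/6.
- At s = 0.1: actual SE = √(0.0032 + 0.0033) = 0.081, which is 1.43 times the reported SE. The nominal 5% test rejects in 2[1 − Φ(1.96/1.43)] = about 17% of studies with no true group difference.
- At s = 0.4: actual SE = √(0.0032 + 0.0533) = 0.238, or 4.2 times, and the rate is about 64%.

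**The case against.** The strongest reply is that silence is not exclusion. The covariate list is not given, country of residence is known for every respondent, and country may well have been in the models. This stands. A reader might infer that country was left out, and might support that with the contrast between individual and country-specific characteristics in the descriptive plan. The documents do not bear that out. In that sentence country is listed separately, and the country-specific wording describes strata such as national income. The adjustment phrase also covers models in which a country grouping is the exposure, where individual-level adjustment is a natural description.

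A reader might also infer that the odds ratios are confounded. That is not established either. Confounding needs country to be related to both exposure and tinnitus, and the documents give no data on either. Check 2 shows that the bias can be nil.

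It can further be said that the objective refers to overall prevalence and that the models look for subgroups where tinnitus is more frequent. For a purely descriptive pooled contrast, a between-country component is not automatically bias. This has some force, but the objectives speak of the effect of personal characteristics and of hearing difficulty, and the plan never says that a mixed contrast is intended.

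None of this answers the remaining gap: someone who follows the written rule would fit a pooled model with no country term, and nothing in the plan tells them otherwise.

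**Conclusion.** The point holds in conditional form. The plan states adjustment for individual-level characteristics only and gives no handling of country in models on data merged from 12 national samples.

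- For individual-level factors, the odds ratios may mix within- and between-country differences. The size cannot be determined from the documents. It ranges from none, when country effects on exposure and tinnitus are absent or unrelated, to a null odds ratio reported as about 0.84 to 1.38 under the widest assumed variation.
- For GDP and region, the intervals would be too narrow if prevalence varies between countries within a group. With an assumed logit SD of 0.1 to 0.4, the false-positive rate of a 6 v 6 contrast would be about 17% to 64% instead of 5%.

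The primary objective, prevalence overall and by country, is not affected by this point.

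**What to change.** In Statistical analyses, list the covariates and state how country enters each model.

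- **Individual-level factors, including hearing difficulty:** include country as 11 indicators, or condition on country. For severe tinnitus, use a sparse-data method (conditional or Firth logistic regression) if a country has few cases. A model without country can be shown as a sensitivity analysis.
- **GDP and region:** country indicators cannot be used, because these groupings are functions of country. Use a country random intercept with a small-sample reference distribution, or a country-level analysis. State that there are only 12 clusters, with only two countries each in the northern (Ireland, England) and western (Germany, France) groups, so these contrasts will be imprecise.

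If country was already in the models, saying so settles the first item.

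Cost: no new data. The 11 degrees of freedom are small against about 1,143 to 1,714 any-tinnitus cases (10% to 15% of 11,427). The text is in the past tense, so the change means rerunning existing models. The intervals for GDP and region will be wider.
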